6.4.3 Methods and scales to be used for the measurement of the variables

Variable	Unity	Symbol	Type	Measuring method	Normal value
Age	Years	--	Continuous	Calculation from the date of birth	NA
Gender	Female/ Male	F / M	Nominal	Direct questioning	NA
Adverse events	Number of cases	n	Discreet	Count	NA
Intraocular pressure	Milimeters of mercury	mmHg	Continuous	Goldman's applanation tonometry	11 - 21
Visual ability	Fraction	Snellen	Nominal	Primer	
Tear rupture time	Seconds	s	Continuous	Direct count	> 10
Eye comfort index	points	--	Discreet	Questionnaire	
	Present / Absent	--	Nominal	Comprehensive valuation	Absent
Vital signs					
Heart rate	Beats per minute	lpm	Discreet	Auscultation	60 – 100
Breathing frequency	Breaths per minute	rpm	Discreet	Auscultation	12 – 24
Systemic blood pressure	Milimeters of mercury	mmHg	Continuous	Non-invasive auscultatory measurement	< 120 / 80
Previous segment					
Ocular surface staining	Degrees	--	Discreet	Direct observation with fluorescein and green lysamin stain	Oxford Scale
Ophthalmologic signs and symptoms					

Variable	Unity	Symbol	Type	Measuring method	Normal value
Conjunctival hyperemia	Normal / Very Light / Mild / Moderate / Severe	--	Ordinal	Direct observation. Classification of Efron.	Normal
Chemosis	Present / Away	--	Nominal	Direct observation	Absent
Burning	Severity: Absent, very mild, mild, moderate and severe	--	Nominal	Direct questioning	Absent
Foreign body sensation	Severity: Absent, very mild, mild, moderate and severe	--	Nominal	Direct questioning	Absent
Pruritus	Frequency: At all times, almost at all times, 50% of the time, almost in no time, at any time	--	Nominal	Direct questioning	Absent
Posterior segment					
Macula	Normal / Abnormal	--	Nominal	Direct observation	Normal
Optical disk integrity	Normal / Abnormal	--	Nominal	Direct observation	Normal
Blood count					
Erythrocytes		M/uL	Continuous		
Hemoglobin	Grams over deciliter	g/dL	Continuous		
Hematocrit	Percentage	%	Continuous		
VGM	Femto liters	fL	Continuous		

Variable	Unity	Symbol	Type	Measuring method	Normal value
HCM	picograms	pg	Continuous		
CMHbG	Grams over deciliter	g/dL	Continuous		
Leukocytes	Thousands per liter units	Mil/uL	Continuous		
Platelets	Thousands per liter units	Mil/uL	Continuous		
Myelocytes	Percentage	%	Discreet		
Metamyelocytes	Percentage	%	Discreet		
Bands	Percentage	%	Discreet		
Segmented	Percentage	%	Discreet		
Lymphocytes	Percentage	%	Discreet		
Monocytes	Percentage	%	Discreet		
Eosinophils	Percentage	%	Discreet		

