6.4.3.1 Visual ability

Visual acuity (VA) is a test of visual function. Spatial visual acuity is the ability to distinguish separate elements of an object and identify them as a whole. It is quantified as the minimum separation angle (located at the nodal point of the eye) between two objects that allows perceiving them as separate objects.

Snellen's notation is described as the distance at which the test is performed, divided by the distance at which the letter is vertically equivalent to 5 arc minutes. Thus, at 6 meters a letter 6/6 (20/20) equals 5 minutes of arc, a letter 6/12 (20/40) equals 10 minutes, and a letter 6/60 (20/200) equals 50 minutes. The Snellen fraction can also be expressed as a decimal (ie $20/20 = 1$ and $20/40 = 0.5$). [26]

The VA will be evaluated basally, without refractive correction with the Snellen chart. Which will be located in a place with adequate lighting, natural or artificial and at a distance of 3m from the subject to be evaluated. The visual acuity of each eye will be taken, starting with a right eye (DO) asking the subject to keep both eyes open and using an occluder to cover the left eye (OS); the subject will read aloud the lines that the evaluator points out, the line of smaller letters that he reaches to see will be annotated by the fractional evaluator as the DO of the DO in the clinical record. Proceed to the OS with the same method.

Subsequently the best refractive correction of the subject will be made and the examination will be repeated using the obtained refraction. This result will be reported as CV, it will be written in fraction in the clinical file and in the CRF, in addition in the CRF it will be written in decimal. By definition, the CV can not be inferior to the AV.

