6.4.3.8 Ocular symptomatology

The subject will be questioned directly about the presence in general (since the last visit) of the following symptoms: burning, foreign body sensation and pruritus. Respond about the severity and frequency of symptoms such as:

Severity: Absent (0), very mild (1), mild (2), moderate (3) and severe (4)

Frequency: At all times (4), almost at all times (3), 50% of the time (2), almost at no time (1), at any time (0).

The number corresponding to each symptom will be registered in the CRF.

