8.3 Statistical methodology

8.3.1 Analysis of primary and secondary outcome variables.

The statistical analysis will be carried out by personnel from Sophia Laboratories, S.A. of C.V The statistical program SPSS version 19 (IBM Corporation, Armonk, NY, USA) will be used.

The designated personnel will be blinded to the intervention groups. The coding will be done using consecutive numbers for each intervention group.

The data will be collected and sorted in an excel sheet. Later they will be exported to the platform of the SPSS program. The variables will be categorized according to their nature.

The result of the continuous quantitative variables will be presented in measures of central tendency: media, standard deviation and ranges. **See Table 6.** Scales to be used

The normal distribution of the results will be obtained by the Kolmogorov-Smirnov test.

The statistical analysis of the continuous **quantitative variables** to find significant differences (p) will be the following:

- Intra-group analysis: Wilcoxon rank test.
- Inter-group analysis: Mann-Whitney U test.

The level of difference to consider significance will be of an alpha of 0.05 or less.

The result of nominal and ordinal qualitative variables will be presented in frequencies, proportions and percentages. See table 1 (section 6.4.3).

The statistical analysis to identify significant differences of the **qualitative variables** will be done by creating 2x2 contingency tables and will be done as follows:

- Intra-group difference: McNemar test.
- Difference between groups: test χ^2 (Chi-square) of Pearson.

The level of difference to consider significance will be of an alpha of 0.05 or less.

For the reporting of adverse events all eyes of those participants who were randomly assigned to an intervention group after the baseline visit will be considered. The results will be expressed in number of cases (eyes).

The final report of the results will be shown in tables or graphs, as appropriate.

It will be considered that the investigational drug is safe and tolerable when there are no clinical and statistical differences in all the variables of primary outcome, with respect to its comparators.

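### Five-level symptom scores, the hyperemia grade and visual capacity go to 2x2 tables with no stated cut-point, although rank tests already in the plan would fit them

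*Combined protocol and SAP*

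**What the plan says.** Section 8.3.1 divides the variables into two classes. Continuous quantitative variables get the Wilcoxon test within groups and Mann-Whitney U between groups. Ordinal variables are put with the nominal ones: "The result of nominal and ordinal qualitative variables will be presented in frequencies, proportions and percentages". For qualitative variables the testing "will be done by creating 2x2 contingency tables", using "Difference between groups: test χ^2 (Chi-square) of Pearson" and "Intra-group difference: McNemar test".

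Table 6 in section 6.4.3 decides which variables fall in which class. It types burning, foreign body sensation, pruritus and visual ability as Nominal, and conjunctival hyperemia as Ordinal. Burning and foreign body sensation have five severity levels and hyperemia has five Efron grades. Pruritus has five levels of a different kind: "Frequency: At all times, almost at all times, 50% of the time, almost in no time, at any time".

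The recording rules show that these variables carry order. Section 6.4.3.8 codes severity and frequency from 0 to 4, asks both for all three symptoms, and ends with "The number corresponding to each symptom will be registered in the CRF". Section 6.4.3.1 has visual capacity written as a fraction and "in addition in the CRF it will be written in decimal".

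Sections 6.4.1.1 and 6.4.1.2 list hyperemia, visual ability and the symptoms as primary outcomes. Section 8.3.1 calls the product safe and tolerable if no primary outcome differs, clinically and statistically, from the comparator.

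**The concern.** A five-level score or a Snellen value enters a 2x2 table only after it has been split in two, and the plan does not say where. Two consequences follow.

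- **The analysis is not defined.** Each score has four possible splits. The choice can be made once the data are visible, and the result can depend on it.
- **The order is thrown away.** Under a general shift towards worse scores, a split usually detects less than a rank test on the whole scale.

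In a superiority trial a weak test works against the sponsor's claim. Here the claim is supported by finding no difference, so a weak test or a convenient cut works in its favour.

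**Working it through.** **1. How each variable is routed**

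| Primary outcome | Recorded as | Type in Table 6 | Test under 8.3.1 | Cut-point stated |
|---|---|---|---|---|
| Burning, foreign body sensation | five levels, 0-4 | Nominal | 2x2 | none |
| Pruritus | five levels, 0-4 | Nominal | 2x2 | none |
| Hyperemia | five Efron grades | Ordinal | 2x2 | none |
| Visual capacity | fraction and decimal | Nominal | 2x2 | none (normal value blank) |
| Chemosis | present or absent | Nominal | 2x2 | not needed |

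Only chemosis fits the test as written. The nearest thing to a cut for the others is the normal value in Table 6 (Absent or Normal) and the objective in 5.5.2, which speaks of the presence of ocular symptoms. Neither is written as an analysis rule.

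**2. Which symptom number is analysed.** Table 6 uses severity for burning and foreign body sensation, and frequency for pruritus. Section 6.4.3.8 asks both for all three and registers one number per symptom. The two sections do not fix the analysed scale.

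**3. Power.** The plan gives no power for these tests, so there is no figure of its own to reproduce. Its sample size (6.6.1) concerns adverse event proportions.

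- From the plan: 15 subjects per arm (6.6.1) and alpha 0.05 (8.3.1), taken as two-sided.
- Assumed: the control distributions over 0-4 and a common odds ratio, because the documents give neither.
- Model: at every cut k, odds of scoring k or more in the shifted arm = odds ratio × the same odds in controls. Example: with 45% of controls absent, the odds of any symptom are 0.55/0.45 = 1.222. At odds ratio 4.5 they become 5.5, so 5.5/6.5 = 84.6% have a symptom and 15.4% are absent.
- Tests: tie-corrected Mann-Whitney by normal approximation, and uncorrected Pearson chi-square. There were 200,000 simulated trials per row, with a simulation standard error of at most √(0.25/200,000) = 0.11 points.

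Power (%):

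| Controls at 0/1/2/3/4 (%) | Odds ratio | Mann-Whitney | 2x2, cut ≥1 | cut ≥2 | cut ≥3 |
|---|---|---|---|---|---|
| 30/30/20/15/5 | 3 | 36.8 | 21.6 | 29.8 | 28.2 |
| | 4.5 | 60.0 | 31.4 | 49.1 | 47.9 |
| 45/25/15/10/5 | 3 | 36.8 | 28.6 | 29.8 | 24.8 |
| | 4.5 | 60.0 | 44.9 | 50.0 | 44.5 |
| 60/20/10/7/3 | 3 | 35.0 | 29.8 | 28.3 | 17.8 |
| | 4.5 | 58.4 | 49.3 | 48.0 | 35.1 |
| 80/10/6/3/1 | 3 | 27.0 | 28.2 | 17.9 | 4.3 |
| | 4.5 | 48.8 | 48.0 | 35.5 | 11.8 |
| 90/5/3/1.5/0.5 | 3 | 17.0 | 17.7 | 6.8 | 0.7 |
| | 4.5 | 33.6 | 35.4 | 16.9 | 2.4 |

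In the first three distributions at odds ratio 4.5, the best cut loses 60.0 − 49.1 = 10.9, 60.0 − 50.0 = 10.0 and 58.4 − 49.3 = 9.1 points. The worst of these cuts loses 28.6, 15.5 and 23.3. With 80-90% of controls absent and the cut absent versus any, the two tests are level to within two points. At the other cuts the loss remains.

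**4. When only severity changes.** Hold absent at 45% and move 45/25/15/10/5 to 45/5/5/20/25. Power is 15% for Mann-Whitney, and 5%, 20% and 46% for chi-square at cuts ≥1, ≥2 and ≥3. A well-placed cut then beats the rank test, while absent versus any has no more than its error rate.

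**The case against.** - **Healthy subjects may mostly score absent.** Eligibility requires ophthalmologically healthy subjects, and absent versus any is the natural reading of 5.5.2 and Table 6. In that case little or no power is lost. This stands, and it rules out saying that the 2x2 analysis always loses power. It does not supply the missing rule.
- **The analyst is blinded to arm (7.4, 8.3.1).** This limits directional cut-picking. Coded groups still show which cut gives a difference. Nothing in the documents suggests that anyone intends a post hoc choice; the plan merely leaves it open.
- **The Summary names chi-square without limiting it to 2x2 tables.** A 2x5 chi-square would need no cut, but it also ignores order. At an assumed odds ratio of 5, with 60% or 40% of controls absent, it has 38-40% power against 64-66% for Mann-Whitney.
- **A shift from mild to severe could be called invisible.** That goes too far. Section 8.3.1 also presents frequencies and percentages, its decision rule mentions clinical differences, and the eye comfort index separately scores frequency and intensity, including itching. What holds is narrower: a test split at absent versus any cannot detect such a shift.
- **Pruritus might seem to have a normal value that is not on its scale.** Section 6.4.3.8 codes 'at any time' as 0, below 'almost at no time' at 1, so it evidently means 'at no time', which is Absent. This is a translation slip. Only the choice between severity and frequency is open.
- **Visual capacity rests on one label.** No section says that it will be dichotomised. That follows only from the word Nominal, which the decimal recording makes unnecessary.
- **The trial is exploratory and the objectives are descriptive.** True, but 8.3.1 still ties a safety conclusion to these tests. Rank tests stay below 80% power in every row above, so they do not cure the low power behind the no-difference rule.

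**Conclusion.** The point holds on the text. Ordered primary outcomes are sent to a test that discards their order and needs an unstated cut, under a rule that rewards finding no difference.

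The size of the power loss is conditional. With 15 per arm, proportional odds and 30-60% of controls at absent, the rank test has 35-37% power against 18-30% at odds ratio 3, and 58-60% against 31-50% at 4.5. The loss is near zero with 80-90% at absent and a cut at absent versus any, and it reverses if only severity moves and the cut is well placed. The documents give no symptom distribution to choose between these cases. The lasting defect is therefore the undefined analysis, whatever the power figure. It should be settled before the database is frozen.

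**What to change.** - **Table 6:** retype burning, foreign body sensation and pruritus as Ordinal, and decimal visual capacity as quantitative.
- **Section 8.3.1:** analyse these and the Efron grade with Mann-Whitney U between arms and the Wilcoxon signed-rank test within arms. Use one prespecified value per subject, for example the worse eye for hyperemia and the two-eye mean for decimal visual capacity.
- **2x2 tables:** keep them for binary items such as chemosis. If a responder table is also wanted for the symptoms, prespecify absent versus any.
- **Table 6 and 6.4.3.8:** reconcile them by naming in advance, for each symptom, whether severity or frequency is the analysed variable. Either can be defended, and it need not be the same for all three.

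The cost is wording in 8.3.1, the Table 6 correction and a check that the CRF captures the named scale. The tests are already in the plan, and no extra subjects or visits are needed. The small downside is lower power than a well-placed cut if only the severity of existing symptoms shifts.

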In general, 0.5% levofloxacin ophthalmic solution has been well tolerated, most of the adverse events related to treatment reported in the studies were of a mild to moderate intensity. In the phase IV study, 42 patients (0.63%) were reported with an adverse reaction, none of which was classified as serious. The reactions that were reported most frequently were: blepharitis, eye irritation, punctate keratitis, keratitis and pruritus; there was only one non-ocular reaction report (contact dermatitis, urticaria and oral numbness).

In the controlled studies, there was no statistical difference between the events reported in the levofloxacin group and control.

The most frequent adverse reactions in the entire study population were: transient decrease in visual acuity, fever, foreign body sensation, headache, transient burning, pain or ocular discomfort, pharyngitis and photophobia. These occurred in approximately 1-3% of patients. Other reported reactions, which occurred in less than 1% of patients, included allergic reactions, eyelid edema, dry eyes and pruritus. [10]

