6.4 Outcome variables

6.4.1 Security variables

6.4.1.1 Primary outcome variables

- Presence of adverse events.
- Intraocular pressure.
- Visual ability
- Laboratory tests: BHc, QS and PFH.
- Ocular surface staining with fluorescein and lissamine green using the Oxford scale.
- Ophthalmological signs: conjunctival hyperemia, chemosis.

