6.6 Sample size

A total size of 30 subjects is estimated, distributed in intervention groups [15 subjects (30 eyes) per group]

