6.6.1 Calculation of the sample size

Although there are no references on the calculation of sample size in phase I studies, it was considered pertinent to perform it according to the presentation of adverse events reported by Schwab IR, et al, in a case-control study in 423 subjects with ophthalmic solutions of levofloxacin 0.5 % and ofloxacin 0.3% for 5 days. [22]

The percentage of adverse events that occurred with the preservative-free HS solution was 7.3%, which is why we consider that at least more than 60% of the exposed subjects will not present this rate of adverse events.

The sample size was calculated using the formula for proportions

$$n = \left[(p_1)(p_2) + (p_1)(p_2) \left(\frac{Z_{1-\alpha}}{2} + Z_{1-\beta} \right)^2 \right] / (p_1 - p_2)^2$$

With a statistical confidence of 95% corresponding to the type I error, equal to 1.96, with a power of 80%, corresponding to the type II error, equal 0.84.

According to the previous calculation, the result is 12.5 subjects (13) per group. The total when considering 2 intervention groups is 26 subjects, which was increased by 20% for the probable losses. The total sample size required is 30 subjects. Therefore, each group will consist of 15 subjects, who will provide both eyes for the analysis, so that the total sample to be analyzed will be composed of 60 eyes.

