The record of the outcome of the adverse event, suspicion of adverse reaction or adverse reaction to medication depends substantially on the follow-up that the principal investigator makes to the participant, since most of the harmful phenomena are expected, consult section of the safety profile in number 5.3 and in the researcher's manual, they are ophthalmic in nature, nevertheless there may be systemic alterations. Therefore, in the opinion of the researcher, the withdrawal of the participant or his / her permanence will be considered, according to the stipulations of section 6.2.2 Exclusion criteria of the present research protocol.

9.3.1.4 Causality evaluation.

The assessment of the causality, the methodology used to estimate the probability of attributing to a drug, investigational drug or investigational product the adverse reaction, the suspicion of the same or the observed adverse event, considers probabilistic categories, according to the evidence available and the quality of information, based on national pharmacovigilance regulations. [33] As a tool to facilitate the probabilistic categorization of causality, the principal investigator can use the algorithm of Karch and Lasagna modified by Naranjo referred to by Aramendi I, 2011 in which different items are qualified which allow assigning a value to the relationship cause-effect between

the administration of the drug and the adverse reaction. [36] See Table 7. Algorithm of Karch and Lasagna modified by Naranjo.

Algorithm of Karch and Lasagna modified by Naranjo.			
No.	Reagent	Score	
		Yes	No
1.	There are previous conclusive reports about the adverse drug reaction, adverse event or suspected adverse drug reaction	+1	0
2.	The adverse event appeared when the suspected drug was administered	+2	-1
3.	Adverse reaction to medication, adverse event or suspected adverse drug reaction improved upon discontinuation or administration of a specific antagonist	+1	0
4.	Adverse reaction to medication / adverse event / suspected adverse drug reaction reappeared when administering the drug / investigational product / investigational medication	+2	-1
5.	There are alternative causes that may cause this reaction	-1	+2
6.	Adverse reaction / adverse event / suspected adverse drug reaction occurred after placebo administration	-1	+1
7.	The drug was determined in blood or other liquids in toxic concentrations	+1	0

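### Adverse-event results are counted in eyes, a unit that gives no defined figure for non-ocular events such as headache or fever

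*Combined protocol and SAP*

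**What the plan says.** Section 6.4.1.1 lists "Presence of adverse events" first among the primary safety outcomes. Section 8.3.1 fixes the reporting set in a sentence that opens "For the reporting of adverse events all eyes of those participants who were randomly assigned to an intervention group after the baseline visit will be", and it fixes the unit in the next one: "The results will be expressed in number of cases (eyes". The eye is treated as the analysis unit in the sample-size sections too: 6.6 gives "15 subjects (30 eyes) per group", and 6.6.1 concludes that "the total sample to be analyzed will be composed of 60 eyes".

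Table 6 (section 6.4.3) gives the unit for adverse events as a number of cases obtained by counting, without saying cases of what. Section 8.3.2 plans no further analyses as a matter of course.

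The same protocol recognises events that have no eye:
- Section 5.3.1.4 names the most frequent reactions to levofloxacin 0.5% as "transient decrease in visual acuity, fever, foreign body sensation, headache, transient burning, pain or ocular discomfort, pharyngitis and photophobia", and adds: "These occurred in approximately 1-3% of patients". It also mentions one non-ocular report comprising urticaria, contact dermatitis and numbness of the mouth.
- Section 6.3.5 gives headache as an example of a reaction that might become more common if drops are instilled more often.
- Section 9.3.1.3 says of harmful events that "they are ophthalmic in nature, nevertheless there may be systemic alterations".

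**The concern.** An eye count works for a red or burning eye. A headache or a fever belongs to a person, and the rule in 8.3.1 makes no exception for it. Someone applying the rule exactly could leave the event out because no eye is affected, enter it once, or enter it twice because both eyes were exposed. All three are defensible from the text, so the figure depends on who codes it.

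This matters because of the conclusion rule in 8.3.1: the product is judged safe and tolerable only if no primary outcome differs, clinically and statistically, from the comparator. A primary outcome whose value is undefined for a recognised class of events cannot support that rule cleanly. The question is separate from how two correlated eyes of one subject should be tested, since a model for paired eyes would still have no value to enter for an event without an eye.

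**Working it through.** **Inputs.** 15 subjects per arm (6.6); both eyes treated (summary, 6.3.1); reporting set of all eyes of randomised participants (8.3.1); background reaction rate of 1% to 3% of patients (5.3.1.4); Pearson chi-square on 2x2 tables for qualitative variables, alpha 0.05 (8.3.1).

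**Step 1. The plan's own figures.** 15 × 2 = 30 eyes per arm and 30 × 2 = 60 eyes in total. Both agree with 6.6 and 6.6.1, so the eye-based denominator for adverse events is 30 per arm.

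**Step 2. One subject with one headache.**

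| Way of counting | Figure | Percentage |
|---|---|---|
| Subject with at least one event | 1/15 | 6.7% |
| Eyes, event omitted (no eye affected) | 0/30 | 0% |
| Eyes, entered once | 1/30 | 3.3% |
| Eyes, both eyes entered | 2/30 | 6.7% |

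The last row matches the subject percentage but shows one event as two cases.

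**Step 3. Could it arise in a trial this small?** Three of the eight reactions listed in 5.3.1.4 are non-ocular (fever, headache, pharyngitis). Assume that the quoted range applies to each reaction and carries over from patients to healthy volunteers. The chance of at least one subject with a given reaction is 1 − (1 − p)^n:
- n = 15: 1 − 0.99^15 = 14%; 1 − 0.97^15 = 37%.
- n = 30: 1 − 0.99^30 = 26%; 1 − 0.97^30 = 60%.

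**Step 4. Does the convention affect the comparison?** Take two affected subjects in one arm and none in the other, treat the outcome as present or absent, and use the uncorrected chi-square, N(ad − bc)² / (product of the four margins):

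| Convention | Table | Chi-square | p |
|---|---|---|---|
| Per subject | 2/15 v 0/15 | 30 × 30² / (15 × 15 × 2 × 28) = 2.14 | 0.143 |
| One eye each | 2/30 v 0/30 | 60 × 60² / (30 × 30 × 2 × 58) = 2.07 | 0.150 |
| Both eyes each | 4/30 v 0/30 | 60 × 120² / (30 × 30 × 4 × 56) = 4.29 | 0.038 |
| Omitted | 0/30 v 0/30 | not computable | none |

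The same two events can therefore fall on either side of 0.05 or disappear. This is an illustration only: the plan does not say that both eyes would be entered, and Table 6 types the variable as a discrete count, so even the choice of test is an assumption.

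**Step 5. Units elsewhere.** The first early-termination condition in 9.2 is a percentage of participants with serious events in each group. The adverse-event result in 8.3.1 is in eyes. The two cannot be read against each other without recounting.

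**The case against.** The best reply is that little is really lost. Section 9.3.1.1 records each event under a subject code, with its type, diagnosis, outcome and affected eye. Section 9.3.1 requires adverse events in the final report, 9.3.1.3 sends non-serious ones to the regulator through that report, and 10.10.1 adopts the ICH E3 format. The product is topical, the study is exploratory with 30 subjects, and the specific objectives on adverse events are to describe. Table 6, read alone, would let a headache count as one case.

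Most of this stands, and it limits the harm. It does not supply the missing unit: a general reference to a report format does not displace an explicit rule in the analysis section, and Table 6 does not give a denominator.

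A reader might also infer more than the documents support:
- *That systemic events would go unrecorded or unreported.* The sections just cited show otherwise.
- *That the protocol predicts systemic events.* Section 9.3.1.3 says the expected events are mostly ocular and only allows for others. Section 6.3.5 mentions headache in the context of overdose.
- *That an abnormal liver test would be hidden.* Laboratory tests are a separate primary outcome in 6.4.1.1 with no eye unit attached.
- *That the result cannot be compared with the 7.3% rate in 6.6.1.* That section does not say the rate is per subject, and no such comparison is planned.
- *That one subject with a headache and a one-eyed event could give three cases out of 30.* This mixes events with eyes; one subject can contribute at most two eyes.

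**Conclusion.** The point holds, confined to the planned tabulation and between-arm comparison. Followed exactly, 8.3.1 gives no defined figure for a symptomatic non-ocular adverse event. For one such event in an arm, the reported value can be 0%, 3.3% or 6.7% of eyes, against 6.7% of subjects.

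That spread needs only the arm size and the wording of 8.3.1. The likelihood of meeting the problem (14% to 37% per arm for any one reaction type) rests on applying the background patient rates to healthy volunteers. The p-values show only that the coding choice is not neutral; they are not a forecast, nor an estimate of the trial's error rate. The correction is worth making because the outcome is primary and feeds the safety conclusion, but the underlying data are not at risk.

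**What to change.** Replace the unit sentence in 8.3.1 with:

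> Adverse events will be reported and compared between arms as the number and percentage of randomised subjects with at least one event, separately for ocular and non-ocular events, together with the number of events. For ocular events the number of affected eyes will be added as a description.

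Change the adverse-event line of Table 6 to the same unit: subjects with at least one event, and number of events. This also puts the result on the participant basis already used in 9.2.

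The cost is one sentence and one table line. No new data are needed, because the case report form already holds the subject code and the affected eye (9.3.1.1).
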